1.5 Study Rationale and Risk Analysis (Risks to Benefits Ratio)

1.5.1 Study Rationale

Data for alternative strategies to prevent stricture formation remain equivocal. The application of ECM, however, appears promising based on preclinical and clinical data, and ECM are FDA approved for use in wound healing. No randomized clinical trials exist.

As an initial step towards assessing the utility of ECM in stricture prevention, we seek to assess the role of ECM in promoting constructive healing following endoscopic resection of esophageal lesions. This will be determined by the ability of a lesion to “lift” with saline injection during routine endoscopic follow-up. The importance of lift was first reported by Uno et al. in colonic lesions.¹⁷ Inability to lift with fluid injection is suggestive of submucosal tumor invasion, but a false-positive nonlift sign may occur after biopsy as a result of the ensuing inflammatory healing process. We hypothesize that the use of ECM in patients undergoing EMR will mitigate this inflammatory process and promote a more constructive model of healing with reformation of the esophageal wall layers as evidenced by a lift sign. Patients receiving ECM will be compared to patients undergoing EMR without application of ECM.

Data from this study may be used to support larger studies investigating the role of ECM in preventing stricture formation in patients undergoing more extensive endoscopic resections via EMR or ESD.

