5.8.4 Return or Destruction of Study Device

We will order clinical supply as needed and dispose of unused supply. We do not anticipate needing to return supplies.

6 Study Procedures

6.1 Visit 1

Patients will be recruited from the Barrett's Esophagus Clinic. Patients referred for endoscopic evaluation of Barrett's esophagus with high grade dysplasia, esophageal nodules or early esophageal cancer and are scheduled for EMR, will be screened using inclusion and exclusion criteria outlined above. Patients meeting inclusion criteria will be consented for study inclusion and will be asked to complete the Mayo Dysphagia Questionnaire.

6.2 Visit 2

Visit 2 refers to the procedure during which the patient will undergo planned EMR of the esophageal lesion. Visits 1&2 may take place on the same date. Patients will undergo endoscopy and those amenable to standard EMR will be randomized to receive ECM or receive standard of care (i.e., observation). ECM will be applied to patients in the manner described above.

6.3 Visit 3

All patients will be scheduled to return in approximately 12-16 weeks (up to 6 months) following EMR for follow-up endoscopic evaluation. Patients will repeat the Mayo Dysphagia Questionnaire prior to endoscopy. During endoscopy, the EMR site will be inspected and multiple pictures will be taken in white-light as well as electron chromoendoscopy (i.e., narrow band imaging). Thereafter, standard submucosal saline injection of the healed EMR site will be performed, and the endoscopist will record whether no lift, a partial lift, or complete lift was observed. Symptomatic structuring will be treated with standard pneumatic dilation.

Schedule of Events			
Study Activity	Baseline*	Procedure*	Follow-up procedure (3-4 months)
Consent	X		
History	X		X
Physical Exam	X	X	X
Disease State Symptom Survey	X		X
Concurrent Medications	X	X	X
Adverse Events		X	X
Serious Adverse Events		X	X

*Baseline and Procedure may be on the same date/visit.

7 Statistical Plan

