7.1 Sample Size Determination

A power analysis was performed for this two independent sample study with a dichotomous endpoint (presence of a saline lift during follow-up EGD). We assume 20% of patients receiving standard of care and no ECM will have a submucosal lift vs. 80% of patients receiving ECM will have submucosal lift. Using a power of 0.8, and alpha of 0.05, this equates to a sample size of 10 for each group for a total of 20 subjects.

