7.2 Statistical Methods

Descriptive Statistics

Univariate descriptive statistics and frequency distributions will be calculated, as appropriate for all variables. Baseline values for demographic, clinical, and outcome variables (primary and secondary) will be tabulated for the treatment groups. These analyses will help identify potential confounding variables to be used as covariates in sensitivity analyses. Distributions across subgroups used in randomization will be compared to assess whether the randomization was successful in equalizing distributions of these prognostic variables across treatment groups. Putative prognostic variables that will be investigated through these descriptive analyses include variables such as presence of submucosal lift, esophageal caliber, need for esophageal dilation, and score on the Mayo Dysphagia Questionnaire.

Handling of Missing Data

Given the small number of patients and minimal follow-up time we do not anticipate missing data.

Primary Hypothesis: To assess the efficacy of ECM products in promoting constructive healing as determined by the ability of the resection site to lift with saline injection during follow-up.

A student unpaired t-test will be performed to compare the incidence of successful lift in the area of prior EMR among ECM and non-ECM groups.

Secondary Hypothesis: Secondary endpoints include efficacy of ECM in preventing symptomatic esophageal stricture formation requiring dilation, preventing dysphagia as determined by questionnaires, and mitigating formation of post-resection scarring as determined by blinded comparison of pre- and post-resection images (taken using white-light endoscopy and electron chromoendoscopy).

Dysphagia questionnaire: student paired t-test will compare the pre and post treatment scores between both groups.

Esophageal diameter: student paired t-test will compare the pre and post treatment sizes between groups.

Interim Analysis

As this is a small pilot study, we will not perform an interim analysis. Any serious adverse events will prompt immediate reevaluation of study methods.

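### Section 7.2 assigns a paired t-test to a comparison between two independent arms, so the planned dysphagia analysis cannot estimate the ECM effect as written

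*Combined protocol and SAP*

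**What the plan says.** Under the secondary hypothesis, Section 7.2 names one test for dysphagia: "Dysphagia questionnaire: student paired t-test will compare the pre and post treatment scores between both groups". It uses the same form for a second variable: "Esophageal diameter: student paired t-test will compare the pre and post treatment sizes between groups".

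The endpoint that the dysphagia test serves, in Sections 3.3 and 7.2, is the efficacy of ECM in "preventing dysphagia as determined by questionnaires". Section 1.5.1 states the comparison of interest: "Patients receiving ECM will be compared to patients undergoing EMR without application of ECM".

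For the primary endpoint, Section 7.2 uses the other term: "A student unpaired t-test will be performed to compare the incidence of successful lift in the area of prior EMR among ECM and non-ECM groups". Section 7.1 describes the design this way: "A power analysis was performed for this two independent sample study with a dichotomous endpoint". Section 5.2 randomizes individual patients by envelope, with stratification and no matching of patients across arms.

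No section gives a change-score comparison, an ANCOVA or any other between-arm test for dysphagia or diameter. Covariates are mentioned only for sensitivity analyses that are not specified.

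**The concern.** The dysphagia sentence contradicts itself. Its purpose is a contrast between groups, but the test it names contrasts two time points in the same patients. Two readings are open.

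1. The authors intend to compare pre-to-post change between arms. That is an unpaired test on change, so only the name is wrong.
2. The paired test is run as named, within each arm or on all patients together. Then there is no arm contrast, and no estimate of the ECM effect comes out of the test.

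Pairing patients across arms is not a third option, because no matching is described.

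Under the second reading, a change that both arms share after EMR could be taken for a device effect, for instance if one arm reaches p<0.05 and the other does not. Section 1.5.1 says that the data may support larger studies. Planning those requires a between-arm difference with its uncertainty, which a pre/post test does not give.

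**Working it through.** **The plan's own figure.** The only computed figure in Section 7 is the sample size for the lift endpoint. With 20% versus 80%, two-sided alpha 0.05, power 0.80, pooled variance and no continuity correction:

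n = [1.96 × √(2 × 0.5 × 0.5) + 0.842 × √(0.2 × 0.8 + 0.8 × 0.2)]² / 0.6² = (1.386 + 0.476)² / 0.36 = 9.6, which rounds up to 10 per group.

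This matches Section 7.1 (power at n = 10 is 81.7%) and confirms that the trial was sized as two independent samples. No figure is given for dysphagia or diameter.

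**What each test estimates.** Let d be a patient's post minus pre score, and let the SD of d be 1.

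- Within-arm paired test (n = 10, 9 df): mean(d) / (s/√10). It asks whether that arm changed over time.
- Pooled paired test (n = 20, 19 df): mean(d) / (s/√20). It asks whether patients as a whole changed over time.
- Unpaired test on change (18 df): [mean(d, ECM) − mean(d, control)] / (s_p × √(2/10)). It asks whether the arms changed by different amounts.

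If both arms shift by δ and ECM has no effect, the noncentrality is δ√10 for the first, δ√20 for the second and 0 for the third. At δ = 0.5 that is 1.58, 2.24 and 0.

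**Assumptions.** The documents give no SD or expected change for dysphagia. The table therefore assumes no ECM effect, 10 analyzed per arm, normally distributed change, two-sided alpha 0.05, and a common shift of 0 to 1.0 SD. With p the rejection probability in one arm (noncentral t), exactly one arm is significant with probability 2p(1 − p), and one particular arm alone with probability p(1 − p).

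| Shared shift (SD of change) | p, one arm | Exactly one arm significant | Pooled paired test rejects |
|---|---|---|---|
| 0 | 0.050 | 0.095 | 0.050 |
| 0.1 | 0.059 | 0.112 | 0.071 |
| 0.2 | 0.088 | 0.160 | 0.136 |
| 0.3 | 0.136 | 0.235 | 0.247 |
| 0.5 | 0.293 | 0.414 | 0.565 |
| 0.7 | 0.506 | 0.500 | 0.844 |
| 1.0 | 0.803 | 0.316 | 0.989 |

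For example, at 0.5 SD: 2 × 0.293 × 0.707 = 0.414. The like-for-like comparator for the third column is 9.5%, not 5%. Half of these results favor ECM: 0.050 × 0.950 = 0.048 at no shift, 0.293 × 0.707 = 0.207 at 0.5 SD, and at most 0.25. The unpaired test on change, simulated with 200,000 trials at each of the shifts 0, 0.2, 0.5 and 1.0 SD, rejects in 5.0% every time.

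**With a real effect.** If the arms change by +0.5 and −0.5 SD (a true difference of 1 SD), simulation with 20,000 trials gives rejection in 3% for the pooled paired test and 56% for the unpaired test on change. The pooled paired test responds to the average change over time and misses the arm difference.

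**Precision after correction.** With 10 per arm, the 95% CI half-width for the difference in mean change is t(0.975, 18 df) × √(2/10) = 2.101 × 0.447 = 0.94 SD of change. Power is 19% at a difference of 0.5 SD, 40% at 0.8 SD and 56% at 1.0 SD. It reaches 80% only at about 1.32 SD.

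**The case against.** The strongest reply is that this is a drafting slip. The sentence itself says that groups are compared, it stands under a hypothesis about ECM efficacy, and the word paired may only mean that each patient's two scores are used. On that reading the error rate is 5% and nothing is lost but clarity. The larger error rates also need three things that the documents do not contain: the literal reading, a shared shift, and someone inferring an ECM effect because only one arm is significant. The pooled figures are tests of change over time, on the reading that the text supports least. Section 7.2 also plans descriptive statistics for all variables, and this is a 20-patient feasibility trial.

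Much of that is fair. The error rates illustrate what the literal reading could do. They do not measure a certain harm. The descriptive statistics soften the gap but do not close it, because tabulation by treatment group is promised explicitly only for baseline values. Some details of scope also stand:

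- Section 3.4 uses the same questionnaires for quality of life, as a primary safety endpoint.
- Section 3.1 adds the Mellow-Pinkas scale, which Section 7.2 does not name.
- Ten analyzed per arm is a best case, given the withdrawals and exclusions in Sections 4.4.1, 5.4 and 7.3.
- Whether diameter is recorded is a separate question from the choice of test. Section 7.2 lists esophageal caliber among the variables to examine, and the case report form is not in the documents.

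What does not stand is leaving the sentence alone. Even on the kindest reading it names the wrong test, in a section that uses paired and unpaired as distinct terms, and no other text settles the matter.

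**Conclusion.** The concern holds. The test named for dysphagia cannot produce the between-arm comparison that its own sentence states, and nothing elsewhere in the documents supplies one. It should be fixed before analysis, so that the reading is not chosen after the data are seen.

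If the authors meant an unpaired test on change, the cost is an ambiguous plan. If the text is followed literally, the trial has no test of the ECM effect on dysphagia. In addition, under the stated assumptions, a shared shift of 0 to 1.0 SD gives a split result between the arms in 9.5% to 50% of trials with no true effect, of which at most 25 percentage points favor ECM.

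The reach is limited to one of the three secondary endpoints in Section 3.3, and to the diameter analysis, which is not a listed endpoint. Stricture needing dilation, scarring, the primary endpoint and the sample size are not affected.

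**What to change.** Replace the dysphagia sentence in Section 7.2 with wording such as:

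> Pre-to-post change in the Mayo Dysphagia Questionnaire score will be compared between the ECM and standard-of-care arms with an unpaired t-test, with an exact rank-sum test as a sensitivity analysis. The between-arm difference in mean change will be reported with a 95% confidence interval. Within-arm pre/post results are descriptive.

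ANCOVA of the follow-up score on arm and baseline score is an acceptable alternative if it is named in advance. The rank-sum test is an addition and is not needed to remove the contradiction. Given the 0.94 SD half-width, the result should be read as an estimate. The same revision can say whether the Mellow-Pinkas scale is analyzed in the same way.

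For dysphagia the cost is wording only. Section 6.1 already collects the baseline questionnaire, and Section 6.3 the follow-up: "Patients will repeat the Mayo Dysphagia Questionnaire prior to endoscopy".

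For esophageal diameter, apply the same between-arm test only if pre and post values are recorded. Sections 6.1 to 6.3 and the Schedule of Events describe no such measurement, so keeping the analysis may add a data item to the visit procedures. Otherwise delete it.

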2.2 Secondary Objective

To assess the efficacy of ECM products in promoting constructive healing as determined by endoscopic inspection via white light and electron chromoendoscopy.

[figure not shown]
3 Study Design

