3.3 Secondary Study Endpoints

Secondary endpoints include efficacy of ECM in preventing symptomatic esophageal stricture formation requiring dilation, preventing dysphagia as determined by questionnaires, and mitigating formation of post-resection scarring as determined by blinded comparison of

pre- and post-resection images (taken using white-light endoscopy and electron chromoendoscopy).

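### Section 7.2 plans a pre/post comparison of esophageal diameter between groups, but the protocol prescribes no diameter measurement and the named paired t-test cannot compare groups

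*Combined protocol and SAP*

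**What the plan says.** The analysis is in section 7.2, under the secondary hypothesis: "Esophageal diameter: student paired t-test will compare the pre and post treatment sizes between groups". Earlier in section 7.2, the putative prognostic variables for descriptive analysis "include variables such as presence of submucosal lift, esophageal caliber, need for esophageal dilation, and score on the Mayo Dysphagia Questionnaire". The plan therefore relies on the variable twice, once as diameter and once as caliber.

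Section 3.3 lists three secondary endpoints: symptomatic stricture that needs dilation, "preventing dysphagia as determined by questionnaires", and scarring judged on blinded images. Section 7.2 repeats that list. The secondary objective in section 2.2 is healing "as determined by endoscopic inspection via white light and electron chromoendoscopy". Diameter appears in none of these.

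At Visit 1 (section 6.1) patients "will be consented for study inclusion and will be asked to complete the Mayo Dysphagia Questionnaire". Visit 2 (section 6.2) covers endoscopy, resection and randomization. For Visit 3 (section 6.3) the text reads "During endoscopy, the EMR site will be inspected and multiple pictures will be taken", followed by the saline injection with a lift grade, and then a sentence on dilation of symptomatic strictures.

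**The concern.** An analysis needs a variable that someone has been told to collect. Here a named test depends on two measurements per patient, and no operational part of the protocol asks for either.

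The pre-resection value is the more exposed of the two. Section 5.2 places randomization immediately after resection, so a value from before resection must be taken at or before the start of the Visit 2 endoscopy. If nobody thinks to record it then, it cannot be taken later.

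The follow-up value has a different weakness. Section 6.3 allows dilation at Visit 3, and sections 1.6 and 3.1 allow patients to return sooner. A diameter read after dilation reflects the dilation as well as the healing.

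Stricture prevention is the motive for the program (section 1.5.1), and the data may support larger trials. A standardized diameter would give those trials an estimate of between-patient variability, which the documents do not contain.

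**Working it through.** **1. Where diameter or caliber is mentioned.** The question is whether the protocol tells anyone to measure it, so the check is a side-by-side reading.

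| Place | What it calls for | Diameter or caliber? |
|---|---|---|
| 2.1, 2.2 Objectives | Lift; endoscopic inspection | No |
| 3.1 General Design | Dysphagia questionnaire and physician scale, inspection, images, saline lift, note of dilations | No |
| 3.2 to 3.4 Endpoints | Lift; stricture needing dilation, dysphagia, scarring on images; safety | No |
| 6.1 Visit 1 | Screening, consent, questionnaire | No |
| 6.2 Visit 2 | Endoscopy, resection, randomization, ECM if assigned | No |
| 6.3 Visit 3 | Questionnaire, inspection, images, lift grade, dilation if symptomatic | No |
| Schedule of Events | Consent, history, physical exam, symptom survey, medications, adverse events, serious adverse events | No |
| 7.2 Descriptive statistics | Caliber named as a variable | Named; no method or time point |
| 7.2 Secondary hypothesis | Pre/post test on diameter | Named; no method or time point |

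The schedule alone would prove little, because it also has no row for saline lift or for images. The difference is that the visit text requires those two and does not require diameter.

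**2. Whether planned images could stand in.** Sections 3.3 and 7.2 use pre- and post-resection images to judge scarring. No scale or sizing method is stated for them, so the documents give no basis for deriving a diameter.

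**3. What the named test does.** Let d = post minus pre for one patient.

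- A paired t-test uses t = mean(d) / (SD(d)/√n) with n − 1 degrees of freedom. It tests whether the mean change is zero in the patients analyzed. Applied to all 20 it ignores arm. Applied within each arm it gives two separate p-values, and neither tests the difference between arms.
- The stated comparison between groups needs t = (mean d in ECM − mean d in control) / (s√(1/10 + 1/10)), where s is the pooled SD of d, with 10 + 10 − 2 = 18 degrees of freedom. ANCOVA of the post value on arm and the pre value is the alternative.

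**4. Scale.** The plan's only sample size figure concerns lift, and it reproduces. With 20% vs 80%, two-sided alpha 0.05 (the plan does not state sidedness), power 0.80, pooled variance and no continuity correction:

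n = [1.96·√(2·0.5·0.5) + 0.8416·√(0.2·0.8 + 0.8·0.2)]² / 0.6² = (1.386 + 0.476)² / 0.36 = 9.6, so 10 per arm. Power at 10 per arm is 0.817.

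That calculation has no bearing on diameter. The documents give no diameter SD, target difference or power, so there is nothing to recompute. For orientation only, with all 10 patients per arm evaluable, a two-sided two-sample t-test on change at alpha 0.05 has 80% power for a difference of about 1.32 SD of the change. Even with the data in hand, the comparison would detect only a large effect.

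**The case against.** The strongest reply is that silence in section 6 and the schedule does not prove non-collection, because neither is a full data list. The schedule omits the primary endpoint, the visit text omits the physician dysphagia scale that section 3.1 requires, and Visit 2 does not mention the pre-resection images that section 3.3 relies on. The case report form is the primary collection instrument (section 9.3) and is not among the documents. Naming caliber in section 7.2 also shows that the authors expected to have it. This stands as a limit on the claim. A reader might infer that the analysis cannot be run, or that 0 of 20 patients will have a diameter; the documents do not support either. What survives is that nothing prescribes or standardizes the measurement.

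A second reply concerns dilation. Section 6.3 puts inspection first, saline injection after it, and mentions dilation last, so a diameter read at inspection would naturally precede dilation at the same visit. That is fair. A reader might go further and infer that the arm with more strictures would come out looking better. A post-dilation value does understate narrowing, but no figure in the documents shows how far, or in which arm, so that reversal is not supported. Dilation before Visit 3 remains unaddressed.

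A third reply is that the stricture question does not depend on diameter. Stricture requiring dilation is a listed endpoint, and section 3.1 has dilations noted. That also stands. Diameter should not be called the one objective measure of narrowing, especially if it would be estimated by eye.

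Finally, a value could be taken after resection but before ECM is placed, within the same endoscopy. That would precede ECM, but it is not a pre-resection value, and the plan does not ask for it either.

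**Conclusion.** The point holds as a gap between the analysis plan and data collection, together with a mismatched test. Section 7.2 commits to a comparison for which the protocol prescribes no measurement, method, level or timing, and the variable is not a listed endpoint. Any values obtained would depend on individual endoscopists recording them unprompted.

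The reach is one secondary analysis; the primary lift endpoint and the listed secondary endpoints do not depend on it. It should be corrected before enrollment, because the pre-resection value has to be taken at or before Visit 2.

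Two assumptions carry the conclusion. The first is that the case report form, which is not available, does not already define the field. The second is that pre treatment in section 7.2 means before resection. If the form does define the measurement, what remains is to bring the protocol text into line and replace the test.

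**What to change.** Choose one of two courses.

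**Keep the analysis.**
- Add one case report form field for luminal diameter at the resection site, with a stated method, unit and level. Estimate it the same way at Visit 2 before resection and at Visit 3 at inspection, before any dilation done at that visit.
- Add the measurement to sections 6.2 and 6.3 and to the Schedule of Events, and list diameter in section 3.3.
- In section 7.2, replace the paired t-test with a two-sample test on change or ANCOVA adjusted for the pre-resection value.
- Flag patients dilated before Visit 3 and state how the analysis accounts for them. Section 3.1 already has dilations noted, so the information will exist.

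**Or delete the diameter analysis** from section 7.2, and remove caliber from the descriptive variables unless it is to be collected.

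The first course costs one field at two endoscopies that already take place, with no new procedure or staff. It sets when a measurement is recorded and leaves decisions about dilation as they are. Its drawback is that a visual estimate is imprecise, which with 10 patients per arm further limits what the comparison can show. The second course costs the diameter result and any variability estimate for a later trial.
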